5.0 STUDY PROCEDURES

Table 5.1 – On-Study Procedures (**see table 5.2 for follow-up procedures)

Time Period	Screening ¹	Inpatient		
		Treatment Administration	Surgery	Post-op ¹²
Informed Consent ¹	X			
Medical history	X			
Physical exam ²	X			X
Karnofsky PS	X			X
Vitals	X	X ³	X	
Toxicity assessment	X	X		X ¹³
Conmeds	X	X		X
MRI ⁴	X			X
CBC with diff ⁵	X	X ⁵		X
Chemistry panel ⁵	X			X
Phosphorus + Mg ⁵	X	X		X
PT/PTT/INR ⁵	X			X
Cholesterol panel ⁵	X			X
Urinalysis	X			
Pregnancy test ⁶	X			
ECG	X			X ⁷
NU-0129 Infusion ⁸		X		
Tumor Resection			X ¹¹	
PK blood samples		X ⁹		
Tissue collection	X ¹⁰			X ¹¹

¹ All screening procedures must be completed within 14 days of registration unless otherwise noted (Labs and pregnancy test must be within 14 days of registration). Informed consent can be within 28 days prior to registration.

² Includes complete neurologic exam and weight. Height will be recorded at screening.

³ Vital signs should include pulse and blood pressure. On the day of treatment administration, vitals will be measured using continuous telemetry immediately prior to, during, and for at least 8 hours post infusion. Vital signs will then be measured at least every 4 hours for a total of 24 hours post-infusion. Vital signs will also be assessed continuously throughout the patient's surgical resection.

⁴ A brain MRI with and without contrast will be performed at baseline (within 21 days of registration) and after surgery as part of standard of care post-op procedures, likely within 48 hours of surgical resection.

⁵ Laboratory tests (including, CBC, Chemistry, PT/PTT/INR, Phosphorus, Mg, and Cholesterol panel) must be drawn within 7 days of registration and treatment. If treatment occurs more than 7 days after the indicated labs, they should be repeated. CBC w/ differential should include WBC, ANC, ALC, and Platelets. A complete chemistry panel will be drawn including Sodium, Potassium, Chloride, Bicarbonate, BUN/Creatinine, AST, ALT, Total Bilirubin, Calcium, and Albumin. CBC with diff will be repeated pre-dose on the day of study treatment.

⁶ A pregnancy test will be performed for females of child-bearing potential at screening (serum or urine) within 14 days of registration.

⁷ An ECG will be performed at screening and only as needed for standard of care toxicity management during post-operative observation.

⁸ NU-0129 will be administered once at 0.04mg/kg IV. The infusion will take place as an inpatient 8-48 hours prior to a planned tumor resection.

⁹ Blood samples will be collected for PK analysis at 1, 3, 5, 10, 30, and 60 minutes (\pm 1 minute), and 4, 8, and 24 hours (\pm 5 minutes) post infusion. See section 9.1 for further details.

¹⁰ Archival tissue will be collected at baseline if the patient has tissue available. See section 9.0 for details.

¹¹ The patient will have a tumor resection surgery, following institutional procedures, 8-48 hours after NU-0129 infusion. Tumor tissue collected during this surgery will be processed for research analysis as outlined in section 9.0 and the lab manual (provided as a separate document).

¹² Standard-of-care post-operative procedures will take place inpatient, including a brain MRI, physical exam, and KPS after surgery, likely within 48 hours of surgery. All other procedures indicated in Table 5.1, including labs, must be completed post-operatively. Patient should be monitored closely for late onset toxicities and discharged only when clinically appropriate. See table 5.2 for study follow-up procedures.

¹³ The tumor should be closely observed for potential discoloration. If discoloration is observed in the tissue, the location, color, and degree of color should be recorded.

Table 5.2 – Follow-Up Procedures

Time from Study Treatment	Follow-Up			
	Day 7 (± 3 days)	Day 14 (± 3 days)	Day 21 (± 3 days)	q 84 days ³ (± 10 days)
Physical exam	X	X	X	X
Karnofsky PS	X	X	X	X
Vitals	X	X	X	X
Toxicity assessment	X	X	X	X ⁵
Commeds ¹	X	X	X	X
Tumor Measurements ²			X ²	X
CBC with diff	X	X	X	
Complete Chemistry panel	X	X	X	
Phosphorus + Mg	X	X	X	
PT/PTT/INR	X	X		
Cholesterol panel	X	X		
Survival status				X ⁴

¹ Concomitant medications will be collected from consent up to 21 days after study drug administration. After 21 days, patients may begin adjuvant treatment for GBM/GS, and such therapies should also be recorded in the patient's study chart.

² Patients will have a brain MRI 21 days (± 10 days) after study drug administration (prior to adjuvant therapy, if applicable) and at least every 84 days (12 weeks) thereafter until disease progression for up to 2 years. If a response is suspected (CR or PR), it should be confirmed with a repeat scan four weeks later per RANO criteria 2011 (see section 6.1).

³ Patients will be followed by routine clinic visit at least every 84 days (12 weeks) for up to 2 years until radiologic disease progression or withdrawal of consent. Post-treatment therapies for GBM/GS during this time should be collected for data purposes.

⁴ After progression, patients will be followed for survival, including subsequent therapies for GBM/GS, for up to 2 years post-treatment. OS and PFS will be analyzed at 6 months post-treatment for all patients.

⁵ If a patient has a continuing adverse event at 21-days post-treatment, the AE should be followed until resolution to ≤ Grade 2 or baseline

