2.0 OBJECTIVES & ENDPOINTS

2.1 Primary Objective & Endpoint

- The primary objective is to assess the safety of intravenous NU-0129 in patients with recurrent GBM or GS.
- The total incidence of adverse events will be evaluated using CTCAE v4.03 from the time of informed consent to 21 days after study drug administration. Adverse events will be monitored during and immediately after the infusion as well as weekly for 21 days after treatment administration.

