4.3 Toxicity Management & Dose Delays/Modifications

Each patient will be assessed for the development of toxicity from the time of consent to 21 days post-dose. Toxicity will be assessed according to CTCAE v4.03. Any patient who receives at least one dose of study therapy will be evaluable for toxicity endpoints.

Patients should be closely observed for infusion-related reactions and any other form of toxicity. Treatment for infusion reactions, and all events, will be based on institutional guidelines. Grading and resolution of the event will be reported using CTCAE v4.03. For example, if a severe infusion reaction occurs, the infusion rate should be cut in half to 2.0-5.0mL/minute.

During the surgical resection, the resected tumor sample should be observed for potential discoloration. The locations and degree of discoloration must be carefully recorded and assessed for relationship to treatment with NU-0129.

There will be no dose delays or modifications as this is a single-dose therapy. However, each patient will be closely monitored for toxicities during the first 21 days after receiving study treatment. Any adverse event that is reported as a Grade 2 toxicity or higher, that is at least possibly related to NU-0129, will be referred to the external DSMB (Data Safety Monitoring Board) for review. The DSMB will review the event within 24 hours of notification to determine a plan for dosing future patients and immediate action if necessary. In addition, each patient's safety data will be reviewed at the end of the 21-day period post therapy and the DSMB will provide a recommendation for future dosing. No additional patients will be registered until the DSMB provides their analysis.

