6.2 Primary Endpoint

Safety will be measured by recording adverse events using CTCAE v4.03 from the time a patient signs consent to 21 days after study drug administration. Any patient who has received at least a partial dose of NU-0129 will be evaluable for this endpoint. If a patient has a continuing adverse event at 21 days which is related to treatment, it will be followed until resolution to baseline or Grade ≤ 2.

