8.1.10 Side effects

As this is a first-in-human trial, side effects in this population are not completely known. In the primate and non-primate treatment trials, a few noted side effects were observed. Gold nanoparticle accumulation in the liver has occurred in some pre-clinical studies as well as skin discoloration following the infusion have been seen with animal models displaying a purple hue to their baseline skin

tone. Hypercholesterolemia was also observed in the non-primate model (rat model).

Possible side effects:

Liver Damage
Skin Discoloration
Infusion Reaction
Hypercholesterolemia
Low blood pressure

There is no significant toxicity associated with the chemistry or manufacturing of the drug product.

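### Adverse events are counted, and the DSMB reviews each patient, to Day 21, but no cholesterol panel is scheduled after Day 14 although hypercholesterolemia is a listed possible side effect

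*Combined protocol and SAP*

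**What the plan says.** Section 2.1 sets the adverse-event window as running "from the time of informed consent to 21 days after study drug administration", with weekly monitoring after treatment. Section 6.2 repeats it, measuring safety by "recording adverse events using CTCAE v4.03 from the time a patient signs consent to 21 days after study drug administration". Section 10.3.1 makes the primary analysis a count of those events.

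Section 4.3 ties the same time point to enrolment. Each patient's "safety data will be reviewed at the end of the 21-day period post therapy", and "No additional patients will be registered until the DSMB provides their analysis".

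On cholesterol itself, Section 8.1.10 states that "Hypercholesterolemia was also observed in the non-primate model (rat model"), and hypercholesterolemia is one of the five entries in its list of possible side effects. Section 3.1.8 also uses cholesterol as an eligibility limit.

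The follow-up schedule in Table 5.2 treats the laboratory tests differently from one another. Chemistry runs through all three early visits ("Complete Chemistry panel X X X"), as do CBC and phosphorus/magnesium. The cholesterol row has only two entries ("Cholesterol panel X X"), at Days 7 and 14, and PT/PTT/INR has the same pattern. Table 5.1 adds cholesterol draws at screening and post-operatively. No blood test is scheduled at the 84-day visits.

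**The concern.** A raised cholesterol normally produces no symptom or sign that an examination or a toxicity interview would pick up, so detecting it depends on a blood test. Section 4.7 says toxicity is monitored by physical examination and the scheduled laboratory tests, and Section 7.2.1 treats an abnormal laboratory finding as an adverse event. If the scheduled test stops before the counting window does, the late part of the window will tend to show no lipid event whether or not one occurred.

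Two uses of the data are affected. The primary safety count could understate lipid events. And the DSMB, whose review decides whether the next patient is registered, would see no scheduled lipid value later than about Day 14. A late Grade 2 or higher rise judged at least possibly related would also not reach the DSMB by the separate event-driven route in Section 4.3, because nobody would have measured it.

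**Working it through.** The plan states no figure of its own on this point. The sample size in Section 10.2 rests on feasibility, with no alpha, power or event rate, so there is nothing to reproduce. The check compares the endpoint window with the visit schedule.

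**Inputs**
- End of the adverse-event window: Day 21 (Sections 2.1 and 6.2).
- Last scheduled cholesterol draw: Day 14 ± 3 days, so Day 11 to Day 17 (Table 5.2).
- Day 21 visit: ± 3 days, so Day 18 to Day 24 (Table 5.2).
- Patients: 6 to 8 (Section 10.2).

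**Does another scheduled test fill the gap?** Footnote 5 to Table 5.1 itemises the chemistry panel: electrolytes, BUN/creatinine, AST, ALT, total bilirubin, calcium and albumin. Cholesterol is not in it, so the Day 21 chemistry draw does not cover it.

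**Is the blank cell real?** In Table 5.2 the tumor-measurement row keeps its leading empty cells, so columns have not shifted in the extracted text. The cholesterol entries belong to Days 7 and 14.

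**Length of the gap** = 21 − day of last draw; share = gap / 21.
- Nominal, last draw on Day 14: 21 − 14 = 7 days; 7/21 = 33.3%.
- Latest permitted draw, Day 17: 21 − 17 = 4 days; 4/21 = 19.0%.
- Earliest permitted draw, Day 11: 21 − 11 = 10 days; 10/21 = 47.6%.

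These shares refer to the 21 post-dose days. The formal window opens at consent, so the share of the whole window is smaller.

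**After adding a Day 21 draw**
- Nominal gap: 21 − 21 = 0 days.
- If the visit falls on Day 18: 21 − 18 = 3 days; 3/21 = 14.3%.
- If the visit falls after Day 21, the window is covered, but Section 4.4.3 allows adjuvant treatment once 21 days have passed. The draw therefore has to be ordered before that treatment, as footnote 2 to Table 5.2 already does for the Day 21 MRI.

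The documents give neither an onset time for the rat finding nor a rate of late onset in any species. The probability of missing an event therefore cannot be derived from them.

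**The case against.** The best defence is that this is a sampling choice and not a contradiction. An adverse-event window says when events are recorded; it does not require every assay on its last day, and Section 4.7 simply refers to the schedule. Any weekly test leaves days between draws. Cholesterol is measured at screening, post-operatively and at Days 7 and 14, so a rise that starts early and persists is caught. Section 7.1 follows a patient with an event until, among other end points, abnormal values return to baseline. A toxicity assessment still takes place at Day 21, and nothing bars an unscheduled test. Late onset is also not suggested by the data: Section 1.2.3 reports no serum chemistry effect in monkeys up to 8 mg/kg, Section 1.2.1 reports half-lives of minutes, and Section 1.3 describes a single micro-dose.

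Most of this stands, and it limits the point to new onset or worsening after the last draw. It does not explain why cholesterol, a listed possible side effect, stops a visit before CBC, chemistry and phosphorus/magnesium. The monkey recovery group ended at Day 14, so it says nothing about the third week.

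Several stronger readings are tempting and are not supported:
- A reader might infer that liver damage, also on the list, goes untested at Day 21. It does not: AST, ALT, bilirubin and albumin are drawn then. PT/PTT/INR also stops at Day 14, but a coagulation abnormality is not among the listed side effects.
- A reader might infer that a late cholesterol rise could never enter the count. An unscheduled test could still find it.
- A reader might take the pigment still present in monkey tissue at Day 14 as a sign of late toxicity. Sections 1.2.2 and 1.2.3 report pigment without cellular or tissue toxicity.
- A reader might say that no value free of adjuvant therapy remains. Day 14 is itself such a value.

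**Conclusion.** The point holds for cholesterol. The count and the DSMB review extend to Day 21, while the last scheduled test for a listed side effect that normally shows only in blood is nominally 7 days earlier (4 to 10 days within the visit tolerance), in all 6 to 8 patients. What can be missed is onset or worsening after that draw when no unscheduled test is done.

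This is a modest mismatch between schedule and endpoint. It is not an arithmetic error, and it does not undermine the safety assessment as a whole. The conclusion assumes that the blank Day 21 cell is intended and that laboratory events are found mainly through scheduled draws, as Section 4.7 indicates. It does not assume that late hypercholesterolemia is likely; the documents do not say either way. The protocol calls the event a possible side effect, and nothing here requires reading it as anticipated at this dose.

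**What to change.** In Table 5.2, mark the cholesterol panel at Day 21. Run it on the blood draw already scheduled for CBC and chemistry, and add a footnote that the sample is taken before any adjuvant therapy starts. PT/PTT/INR could go on the same draw for consistency, but that is secondary.

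The cost is one routine assay per patient, 6 to 8 in total, plus a table edit. There is no new visit or separate blood draw, and no change to the sample size or analysis.

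If the sponsor prefers to keep the present schedule, the protocol should state why Day 14 is sufficient. The DSMB summary and the final report should then say that any absence of lipid events rests on scheduled draws to about Day 14, not on measurements to the end of the window.

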6.0 ENDPOINT ASSESSMENT

6.1 Definitions

6.1.1 RANO Criteria 2010 [18]

Table 6.1. Criteria for Response Assessment Incorporating MRI and Clinical Factors

Response	Criteria
Complete response	Requires all of the following: complete disappearance of all enhancing measurable and nonmeasurable disease sustained for at least 4 weeks; no new lesions; stable or improved nonenhancing (T2/FLAIR) lesions; patients must be off corticosteroids (or on physiologic replacement doses only); and stable or improved clinically. Note: Patients with nonmeasurable disease only cannot have a complete response; the best response possible is stable disease.
Partial response	Requires all of the following: $\geq 50\%$ decrease compared with baseline in the sum of products of perpendicular diameters of all measurable enhancing lesions sustained for at least 4 weeks; no progression of nonmeasurable disease; no new lesions; stable or improved nonenhancing (T2/FLAIR) lesions on same or lower dose of corticosteroids compared with baseline scan; the corticosteroid dose at the time of the scan evaluation should be no greater than the dose at time of baseline scan; and stable or improved clinically. Note: Patients with nonmeasurable disease only cannot have a partial response; the best response possible is stable disease.
Stable disease	Requires all of the following: does not qualify for complete response, partial response, or progression; stable nonenhancing (T2/FLAIR) lesions on same or lower dose of corticosteroids compared with baseline scan. In the event that the corticosteroid dose was increased for new symptoms and signs without confirmation of disease progression on neuroimaging, and subsequent follow-up imaging shows that this increase in corticosteroids was required because of disease progression, the last scan considered to show stable disease will be the scan obtained when the corticosteroid dose was equivalent to the baseline dose.
Progression	Defined by any of the following: $\geq 25\%$ increase in sum of the products of perpendicular diameters of enhancing lesions compared with the smallest tumor measurement obtained either at baseline (if no decrease) or best response, on stable or increasing doses of corticosteroids*; significant increase in T2/FLAIR nonenhancing lesion on stable or increasing doses of corticosteroids compared with baseline scan or best response after initiation of therapy* not caused by comorbid events (eg, radiation therapy, demyelination, ischemic injury, infection, seizures, postoperative changes, or other treatment effects); any new lesion; clear clinical deterioration not attributable to other causes apart from the tumor (eg, seizures, medication adverse effects, complications of therapy, cerebrovascular events, infection, and so on) or changes in corticosteroid dose; failure to return for evaluation as a result of death or deteriorating condition; or clear progression of nonmeasurable disease.

NOTE. All measurable and nonmeasurable lesions must be assessed using the same techniques as at baseline.
 
Abbreviations: MRI, magnetic resonance imaging; FLAIR, fluid-attenuated inversion recovery.
 
*Stable doses of corticosteroids include patients not on corticosteroids.
	

These RANO Criteria are also summarized in Table 6.2:

Table 6.2 Summary of the RANO Criteria

	CR	PR	SD	PD#
T1-Gd +	None	≥50% decrease	<50% decrease but ≤ 25% increase	≥25% increase*
T2/FLAIR	Stable or decrease	Stable or decrease	Stable or decrease	Increase*
New Lesion	None	None	None	Present*
Corticosteroids	None	Stable or decrease	Stable or decrease	NA**
Clinical Status	Stable or improve	Stable or improve	Stable or improve	Deterioration*
Requirement for Response	All	All	All	Any*

CR=complete response; PR=partial response; SD=stable disease; PD=progressive disease

*: Progression when this criterion is met **: Increase in corticosteroids alone will not be taken into account in determining progression in the absence of persistent clinical deterioration

6.2 Primary Endpoint

Safety will be measured by recording adverse events using CTCAE v4.03 from the time a patient signs consent to 21 days after study drug administration. Any patient who has received at least a partial dose of NU-0129 will be evaluable for this endpoint. If a patient has a continuing adverse event at 21 days which is related to treatment, it will be followed until resolution to baseline or Grade ≤ 2.

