4.6 Duration of Therapy

Within 14 days of study registration, patients will receive intravenous NU-0129 one time at nominal dose 0.04mg/kg. Patients will be admitted the morning of the planned NU-0129 infusion, and a tumor resection will occur 8-48 hours after administration. Patients will remain inpatient for standard of care post-operative procedures, including an MRI of the brain. Discharge will take place when clinically appropriate.

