7.2 Definitions & Descriptions

7.2.1 Adverse Event

An adverse event (AE) is any untoward medical occurrence in a patient receiving study treatment and which does not necessarily have a causal relationship with this treatment. An AE can therefore be any unfavorable and unintended sign (including an abnormal laboratory finding), symptom, or disease temporally associated with the use of an experimental intervention, whether or not related to the intervention.

Recording of AEs should be done in a concise manner using standard, acceptable medical terms. In general, AEs are not procedures or measurements, but should reflect the reason for the procedure or the diagnosis based on the abnormal measurement. Preexisting conditions that worsen in severity or frequency during the study should also be recorded (a preexisting condition that does not worsen is not an AE). Further, a procedure or surgery is not an AE; rather, the event leading to the procedure or surgery is considered an AE.

If a specific medical diagnosis has been made, that diagnosis or syndrome should be recorded as the AE whenever possible. However, a complete description of the signs, symptoms and investigations which led to the diagnosis should be provided. For example, if clinically significant elevations of liver function tests are known to be secondary to hepatitis, "hepatitis" and not "elevated liver function tests" should be recorded. If the cause is not known, the abnormal test or finding should be recorded as an AE, using appropriate medical terminology (e.g/ thrombocytopenia, peripheral edema, QT prolongation).

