10.3 Data Analyses Plans**10.3.1 Primary Objective**

To evaluate the safety of NU-0129 SNA gold nanoparticle infusion in patients with recurrent GBM or GS, we will count and record the number of adverse events.

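### The primary safety result is planned as a count of adverse events in a window that opens at consent, so as written it can include pre-drug events and does not show how many dosed patients were affected

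*Combined protocol and SAP*

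**What the plan says.** Three sections of the combined protocol and SAP set the window for the primary endpoint, and all three open it at consent and close it 21 days after dosing.

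- Section 2.1: "The total incidence of adverse events will be evaluated using CTCAE v4.03 from the time of informed consent".
- Section 4.3: "Each patient will be assessed for the development of toxicity from the time of consent to 21 days post-dose".
- Section 6.2: safety is measured by "recording adverse events using CTCAE v4.03 from the time a patient signs consent to 21 days after study drug administration".

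The planned primary analysis is a single sentence in section 10.3.1: "we will count and record the number of adverse events". Section 10 has no definition of a treatment-emergent event, no split by onset, and no tabulation by patient, grade or attribution.

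Two provisions fix how early consent may fall. Table 5.1, footnote 1: "Informed consent can be within 28 days prior to registration". Section 4.6: "Within 14 days of study registration, patients will receive intravenous NU-0129 one time".

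Other text bears on the point:

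- Section 2.1 goes on to place active monitoring during the infusion, just after it, and then weekly to day 21.
- Section 7.2.1 opens its definition with "An adverse event (AE) is any untoward medical occurrence in a patient receiving study treatment". It also asks for a link in time to the use of the intervention, and leaves out pre-existing conditions that do not worsen.
- Section 6.2 makes every patient who received at least part of a dose evaluable for safety.
- Sections 4.3 and 7.3.2 call for a judgement of relatedness.
- Section 4.6 puts the resection 8 to 48 hours after the infusion.

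**The concern.** Collecting events from consent is ordinary practice. The difficulty is that the analysis has the same scope as the collection. Events that start between consent and infusion cannot have been caused by NU-0129, yet nothing in 10.3.1 keeps them out of the total. The length of that interval depends on scheduling and differs between patients, so the total depends partly on when people happened to consent.

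An event total also cannot tell one patient with many events from many patients with one event each. Section 2.1 speaks of incidence, which could mean patients, but 10.3.1 plans only the number of events. Section 10.2 defends the sample size by saying that the primary outcome can be estimated precisely enough. That statement is hard to assess until the primary outcome is expressed as a proportion of the evaluable patients. With 6 to 8 patients in a first-in-human study, a few misplaced events can change the reported picture.

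**Working it through.** The plan gives no event rate, interval or target precision, so there is no figure to reproduce. The checks below use the plan's own windows. Where a rate or count is needed, it is marked as assumed.

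**1. Length of the pre-drug window.** Inputs: at most 28 days from consent to registration (Table 5.1, footnote 1), at most 14 days from registration to dosing (4.6), and 21 days after dosing (2.1, 4.3, 6.2). The ceiling is 28 + 14 = 42 days. Pre-drug share of the window = pre / (pre + 21).

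| Pre-drug days | Whole window | Pre-drug share |
|---|---|---|
| 42 (ceiling) | 63 | 67% |
| 28 | 49 | 57% |
| 21 | 42 | 50% |
| 14 | 35 | 40% |
| 2 | 23 | 9% |

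These are shares of calendar time, not of events.

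**2. Where assessments fall.** Up to day 21 the schedule has six toxicity assessments: screening, treatment and post-operative (Table 5.1), and days 7, 14 and 21 (Table 5.2). Only screening is clearly pre-drug: 1/6 = 17%. Since "All screening procedures must be completed within 14 days of registration unless otherwise noted", that visit may fall up to 14 + 14 = 28 days before dosing. By scheduled contact, ascertainment is weighted towards the post-drug period, against the 2:1 ratio of days (42:21) at the ceiling.

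**3. What the windows could do to a total (assumed rates).** Suppose a constant background of b events per patient per 28 days and no drug effect. Expected pre-drug events = n × b × pre / 28; expected total = n × b × (pre + 21) / 28. For n = 8:

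| Lead-in | b | Pre-drug events | Total |
|---|---|---|---|
| 42 days | 0.5 | 8 × 0.5 × 42/28 = 6 | 8 × 0.5 × 63/28 = 9 |
| 42 days | 2 | 24 | 36 |
| 7 days | 0.5 | 8 × 0.5 × 7/28 = 1 | 8 × 0.5 × 28/28 = 4 |
| 7 days | 2 | 4 | 16 |

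This shows how the total depends on lead-in; it is not a forecast. Any post-operative excess of events would lower the pre-drug share.

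**4. What a total hides (assumed count).** This bears only on the form of the count, not on pre-drug events. Seven events among seven dosed patients fits 1/7 affected (14%, exact 95% CI 0.4% to 57.9%) or 7/7 (100%, 59.0% to 100%). Limits are Clopper-Pearson; for 7/7 the lower limit is 0.025^(1/7) = 59.0%.

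**5. What a per-patient measure would allow.** With a fixed 21-day post-infusion window and the section 6.2 patients as denominator, precision can be stated. If no patient has an event, the upper 95% limit is 1 − 0.025^(1/n): 45.9% for n = 6, 41.0% for n = 7 and 36.9% for n = 8.

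**6. Surgery inside the post-drug window.** 21 days is 504 hours. Resection at 8 to 48 hours leaves 8/504 = 1.6% to 48/504 = 9.5% of that window before surgery. A split at infusion removes pre-drug events but does not separate surgical ones.

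**The case against.** The strongest reply is that the plan already means on-treatment events. The monitoring named in 2.1 for the primary endpoint is all during or after the infusion. Adverse event is a defined term, and 7.2.1 ties it to a patient receiving treatment and to timing relative to the intervention. The screening toxicity assessment can serve as the baseline that the worsening rule needs, and the SAE rule in 7.2.3, which runs from consent whatever the attribution, governs reporting rather than analysis.

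This stands as evidence that the intent is unclear. It does not settle the matter. A monitoring schedule and a definition do not override three explicit consent-start windows, and neither says which events enter the count. The rule on unchanged pre-existing conditions does not reach new events between consent and infusion. If 7.2.1 is meant to govern, it conflicts with 2.1, 4.3 and 6.2, and the sections still need reconciling.

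A second reply is that grade, attribution and patient-level data will exist, so with 6 to 8 patients any table can be made. That is right about the data and is why the remedy is cheap. It does not make the table part of the plan.

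A reader might also infer that the endpoint has no denominator at all. The documents do not support that: 6.2 defines the evaluable patients. What is missing is a statement in 10.3.1 that the result is the number and percent of those patients with an event.

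**Conclusion.** The point holds as a gap in the analysis plan, not in data collection, and should be fixed. Read as written, the primary result can include events from up to 42 days before dosing, and it does not report how many dosed patients were affected. The 42 days require both intervals to run to their limits. Actual lead-in times and event numbers are not given, so the size of any distortion is unknown.

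Two stronger conclusions are tempting and should not be drawn.

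- A reader might infer that about two thirds of the counted events will be pre-drug. The 67% is calendar time at the ceiling, and scheduled assessments are weighted towards the post-drug period.
- A reader might infer that patient protection is weakened. Under 4.3, DSMB referral rests on events of Grade 2 or higher that are at least possibly related, and each patient's data are reviewed at the end of the 21 days before anyone else is registered. Neither step uses the 10.3.1 count. No hypothesis test is tied to it either.

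The effect is confined to the reported descriptive primary result.

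A related wording point: the Summary, and 10.3.3 in softer terms, describe an analysis set of patients who undergo surgery. This does not show that dosed patients without resection are lost to the safety analysis, since 4.9 and 6.2 keep them evaluable. The wording should still agree.

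**What to change.** Keep collecting events from consent, and change the analysis text.

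- In 10.3.1, make the primary table the number and percent of patients given any amount of NU-0129 (the set already in 6.2) with at least one event that starts or worsens from start of infusion to day 21, by worst grade and attribution. Show the event count beside it.
- In that table, flag onset before or after the start of resection.
- List consent-to-infusion events separately.
- Reconcile 2.1, 4.3, 6.2 and 7.2.1, so that it is clear which events are collected and which enter the primary result.
- In the Summary and 10.3.3, limit the surgery-based set to the non-safety endpoints, in line with 4.9. Align the 4.3 wording on at least one dose with the 6.2 wording on a partial dose.

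The cost is wording and minor extra tabulation; sample size and visits do not change. Grade and attribution are already required, and infusion start and stop times are logged (8.1.11). The split depends on recorded onset dates, with clock times on the infusion day and the day of surgery. The documents do not show the eCRF, so this should be confirmed.
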